5.8.5 ECG

The overall central evaluation of ECGs will be summarised and listed. The overall central evaluation of ECG data will be presented using shift tables. However, only presenting summaries of the total, tralokinumab naïve, re-treated, and continuously treated, not the washed-out subjects.

All other ECG parameters collected will be listed.

5.8.6 Anti-drug antibodies

The ADA status categories are updated compared to the CTP Section 14.3.8.4 to incorporate ADA data from the parent trial.

The ADA status will be categorized as below, where all ADA assessments from the parent trial and ECZTEND are taken into account. For subjects who received tralokinumab treatment in the parent trial, 'first tralokinumab dose' refers to the first tralokinumab dose in the parent trial, if applicable.

The ADA status will be categorised as follows:

ADA positive

- Pre-existing: At least 1 positive ADA assessment before first tralokinumab dose, no post-tralokinumab ADA response greater or equal to 4-fold over the maximum pre-tralokinumab titre level. At least 1 positive post-tralokinumab ADA assessment.
- Treatment-boosted: At least 1 positive ADA assessment before first tralokinumab dose, at least 1 post-tralokinumab ADA response greater or equal to 4-fold over the maximum pre-tralokinumab titre level.
- Treatment-emergent: All ADA assessments negative or missing before first tralokinumab dose, at least 1 positive ADA response after first tralokinumab dose.
 - Persistent: Positive ADA for at least 2 consecutive visits at least 10 weeks apart.
 - Indeterminate: Only the last ADA response positive.
 - Transient: Neither persistent nor indeterminate.

ADA negative

• All ADA assessments negative or missing. At least one non-missing ADA assessment after first tralokinumab dose.

Perishing ADA

• At least 1 positive ADA assessment before first tralokinumab dose, all ADA assessments negative after first tralokinumab dose.

No post-baseline

• No ADA assessments after first tralokinumab dose.

For subjects with an ADA positive measurement during the trial, the development in EASI and neutralising antibodies (nAB) will be presented graphically and listed (IGA included).

Presentations will only present the total, tralokinumab naïve, re-treated, and continuously treated, not the washed-out subjects.

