EuroQoL 5-Dimension Health Questionnaire 5-Level ⁸			X			X	X		X	X	11.3.2.3	
Worst Weekly Pruritus numeric rating scale ⁹ Eczema-related Sleep numeric rating scale ⁹ Patient use of topical treatment ¹⁰	X	X	X	X	X	X	X		X	Х	11.3.2.4	

- 1) Subjects who withdraw from the trial will be followed up as described in Section 10. The final safety follow-up visit will be 16 weeks after the last dose (i.e. 14 weeks after the EOT visit).
- 2) The number of weeks until the EOT visit (2 weeks after the last dose of tralokinumab, maximum 140 weeks) and SFU visit (maximum 154 weeks) for each subject will depend on the time of their trial entry and treatment duration.
- 3) Assessments and procedures to be performed at an unscheduled visit are at the discretion of the investigator. If the unscheduled visit involves administration of rescue treatment, the investigator should make every attempt to conduct efficacy and safety assessments (at least disease severity scores [IGA and EASI], concomitant medications/procedures, and AEs) immediately before administering any rescue treatment (see Section 9.5).
- 4) If the date of a trial visit does not conform to the clinical trial protocol, subsequent visits should be planned to maintain the visit schedule relative to baseline.

Trial ID: LP0162-1337

5) At trial visits, tralokinumab will be injected at the trial site, preferably by the subject or their caregiver, alternatively by site staff. At each trial visit, subjects will be provided with tralokinumab to be administered at home until the next trial visit. In case of intercurrent illness that may compromise the safety of the subject, or fever within 72 hours prior to administration, tralokinumab administration should be rescheduled. If an anaphylactic reaction occurs, blood samples should be drawn for the analysis of serum tryptase (see details in Section 9.2).

- 6) Urine samples will be tested at the trial site (dipstick). In case of abnormal dipstick results, a urine sample will be sent to the central laboratory for microscopic examination (leucocytes, erythrocytes, and casts) (Section 11.4.5).
- 7) Adult subjects from all parent trials, except the LP0162-1334 trial, will perform the DLQI. Subjects from the parent trial LP0162-1334 will perform the CDLQI, independent of the age of the subject during participation in ECZTEND.
- 8) Subjects from the parent trial LP0162-1334 will not perform the EuroQoL 5-Dimension Health Questionnaire 5-Level.

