Weeks since first treatment in LP0162- 1337	-2	0	2	4	8	16	24	32 64 96 128 160 192 224 256	40 72 104 136 168 200 232 264	48 80 112 144 176 208 240	56 88 120 152 184 216 248	Variable ² (max 268)	SFU visit Variable ²	Un- scheduled visit (if applicable) ³	Early termination (if applicable) ¹	References (protocol section)
Visit type	Site	Site	Site	Site	Site	Site	Site	Tele- phone ⁴	Short Site	Tele- phone ⁴	Standard Site	Site	Site			
Visit window (days) ⁵	-3	NA	±3	±3	±3	±3	±3	±3	±3	±3	±3	±3	±3			
Patient-reported	d outcom	es (cont	inued)													
Worst Weekly Pruritus numeric rating scale Eczema-related																
Sleep numeric rating scale	X	X	X	X	X	X	X		X		X	X		X	X	11.3.2.4
Patient use of topical treatment ¹⁴																

- 1) If screening/baseline visits are performed on the same day as visit(s) in the parent trial, the order of assessments should be adhered to, working in parallel for both protocols. Assessments where data are captured in different vendor systems databases (ECG, ePRO, and laboratory tests) need to be completed twice. In such cases, the parent trial assessment should be performed first, followed by the trial LP0162-1337 assessment. For subjects included in the trial prior to protocol version 10, the first visit after May 2021 can be a site visit or a telephone visit.
- 2) Subjects who withdraw from the trial will be followed up as described in Section 10. The final safety follow-up visit will be 4 weeks after the last dose (i.e. 2 weeks after the EOT visit). For subjects from the parent trial LP0162-1334, the maximum number of weeks until the EOT visit will be 114 weeks.
- 3) Assessments and procedures to be performed at an unscheduled visit are at the discretion of the investigator. If the unscheduled visit involves administration of rescue treatment, the investigator should make every attempt to conduct efficacy and safety assessments (at least disease severity scores [IGA and EASI], concomitant medications/procedures, and AEs) immediately before administering any rescue treatment (see Section 9.5).

Trial ID: LP0162-1337

THIS DOCUMENT CONTAINS CONFIDENTIAL INFORMATION AND MUST NOT BE COPIED OR MADE AVAILABLE TO ANY THIRD PARTY WITHOUT THE PRIOR WRITTEN CONSENT OF THE LEO PHARMA GROUP

- 4) For subjects from the parent trial LP0162-1334, the telephone visit should preferably be performed as a video call.

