7.1.3.2 Treatment period until end of May 2021 (all subjects)

All subjects included in the trial prior to protocol version 10, attended site visits every 8 weeks until the last visit before end of May 2021, and followed the schedules of trial procedures in Section 4.1.

At end of May 2021, the procedures applicable depended on whether the subjects did NOT or DID accept to continue in the trial after May 2021:

- Subject did NOT re-consent to continue in the trial after May 2021:
 The subject continued to follow the trial procedures in Section 4.1. The subject had to be supplied with IMP for home dosing until end of May 2021, where treatment had to be stopped.
- Subject DID re-consent to continue in the trial after May 2021:

 After signing the consent form (subject or legal authorised representative), as well as the assent form for adolescent subjects, the last visit before end of May 2021 had to be completed as a normal site visit (i.e. not as an EOT visit). After that, the schedule of trial procedures in Section 4.2 was followed (see description of treatment period after May 2021 in Section 7.1.3.3).

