7.1.3.3 Treatment period after May 2021

Subjects who wanted to participate in the trial after May 2021 had to re-consent (subjects included based on earlier protocol versions than version 10) or consent (subjects included based on protocol versions 10 to 12) to participate.

Subjects who re-consented/consented to participate in the trial after May 2021 follow the modified schedule of trial procedures specified in Section 4.2:

• For subjects included in the trial based on protocol versions 10 to 13, treatment will be initiated as described in Section 7.1.3.1.

Page 52 of 187

• For subjects included in the trial prior to protocol version 10, the first visit after May 2021 can be a site visit or a telephone visit. The first site visit may be after 8 weeks before starting the 16-week schedule to align individual visit schedules with endpoints.

- All subjects who re-consented/consented to participate in the trial after May 2021: subjects will start with a 24-week period with more frequent visits, and then continue with site visits (standard site visits or short site visits) every 16 weeks, interchanging with a telephone visit in between the site visits. For subjects from the parent trial LP0162-1334, the telephone visit should preferably be a video call. Visit types during the treatment period are described in Section 7.1.3.4.
- Treatment completion dates are dependent on the subject's consent and are done according to Panel 7.

Panel 7 Treatment completion date

Parent trial	Subject did NOT consent to continue after May 2021	Subject DID re-consent or consent to participate after May 2021
LP0162-1325, -1326, -1339, -1341, -1342, -1343, -1346, and TRA-WEI-0015-I	End of May 2021	Country-specific end date according to Appendix 3J
LP0162-1334 (adolescents)	End of May 2021	End of May 2022

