10.3 Early termination assessments

Withdrawal from trial

Subjects withdrawn from the trial for any reason should attend an early termination visit as soon as possible after the last administration of IMP and should return to the trial site for a safety follow-up visit after last administration of IMP as specified in Section 7.1.4. See the schedule of trial procedures (Section 4) for data to be collected at an early termination visit. The investigator will review any AEs, which will be followed up according to Section 13.7, if the subject agrees. An EOT (end of treatment) form and an end of trial form must be completed as specified in Section 11.8. No EOT visit is to be done for subjects who are withdrawn from trial.

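### SAP 5.8.6 labels treatment-emergent ADA 'transient' when the only positives are the last two or more samples within 10 weeks, although no later negative sample exists (minor)

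*SAP*

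**What the plan says.** SAP 5.8.6 gives three subcategories for treatment-emergent subjects, that is, those with no positive sample before the first tralokinumab dose and at least one after it:

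- The first label needs two positives well separated in time: "Persistent: Positive ADA for at least 2 consecutive visits at least 10 weeks apart".
- The second is for a lone positive at the end: "Indeterminate: Only the last ADA response positive".
- The third takes whoever is left: "Transient: Neither persistent nor indeterminate".

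Protocol 14.3.8.4 has the same three rules and plans a whole-trial table by them. Protocol section 12 says that immunogenicity is evaluated to the end of safety follow-up.

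ADA is sampled at end of treatment (EOT), early termination and safety follow-up (SFU) (protocol Panels 4 and 5). EOT is 2 weeks after the last dose. The timing of SFU depends on the schedule:

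- After May 2021 (protocol 4.2): "The final safety follow-up visit will be 4 weeks after the last dose (i.e. 2 weeks after the EOT visit".
- Until end of May 2021 (protocol 4.1): "The final safety follow-up visit will be 16 weeks after the last dose (i.e. 14 weeks after the EOT visit".

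Withdrawn subjects have no EOT visit. Under protocol 10.3, "Subjects withdrawn from the trial for any reason should attend an early termination visit as soon as possible after the last administration of IMP", and SFU follows.

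**The concern.** 'Transient' is a residual label that requires no negative sample after the positives. In ordinary use it says that the antibody appeared and went away. Under these rules it also covers subjects still positive at the last sample taken, provided that the preceding sample was positive too and the run is shorter than 10 weeks. The order of the labels is then perverse: a single positive at the last sample is 'indeterminate', and a second positive just before it, which is more evidence of continuing antibody, moves the subject to 'transient'.

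The trial's schedule produces this pattern. After May 2021 the last two planned ADA samples lie 2 weeks apart, while the persistent rule needs 10. At stake is how the treatment-emergent subcategory table reads: some antibodies still present at the end of observation would be reported as transient.

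**Working it through.** **Inputs.** Persistent threshold: 10 weeks = 70 days (SAP 5.8.6). EOT: 2 weeks after the last dose. SFU: 4 or 16 weeks after the last dose (protocol 4.1, 4.2 and Panel 8). Windows: ±3 days at EOT and at SFU (Panels 4 and 5). Assumption: all earlier samples, including those from the parent trial, are negative.

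**The protocol's own intervals.** EOT to SFU is 4 − 2 = 2 weeks on the new schedule and 16 − 2 = 14 weeks on the old one. Both agree with the protocol.

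**4-week follow-up.**

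1. First positive at EOT, SFU positive: 14 ± 6 = 8 to 20 days. This is below 70, so not persistent. Two samples are positive, so not indeterminate. The label is transient in every in-window combination.
2. First positive at early termination, SFU positive: the longest gap arises when early termination is on the day of the last dose, 28 + 3 = 31 days. Always transient.
3. Preceding ADA visit, EOT and SFU all positive, with EOT 2 to 6 weeks after that visit: the run spans 4 to 8 weeks, at most 56 + 6 = 62 days. Transient.
4. As in step 3, but with EOT 8 weeks after the preceding visit: the run spans 70 ± 6 = 64 to 76 days. The label then depends on the windows and on whether the 10 weeks refer to the whole run or to adjacent samples, which the SAP does not say.

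**Example** (Panel 5 samples at Weeks 4, 16, 56 and 88, EOT at Week 92, SFU at Week 94, nominal dates):

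| Positive samples | SAP label | Label under the fix below |
|---|---|---|
| 94 only | indeterminate | indeterminate |
| 92, 94 | transient | indeterminate |
| 88, 92, 94 | transient | indeterminate |
| 56, 88, 92, 94 | persistent | persistent |

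**16-week follow-up.**

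- EOT and SFU both positive: 98 ± 6 = 92 to 104 days, always persistent.
- Early termination has no fixed window. If it is held less than 10 weeks before SFU, that is, more than 16 − 10 = 6 weeks after the last dose, a positive pair is transient.
- If SFU is missed, a positive scheduled ADA visit followed by a positive EOT 2 to 8 weeks later (at most 56 + 6 = 62 days) is transient.

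**Which EOT weeks qualify.** This depends on the subject's own sampling weeks. Subjects included before protocol version 10 "attended site visits every 8 weeks until the last visit before end of May 2021", with ADA samples on the Panel 3 and 4 weeks, and moved to the Panel 5 weeks if they re-consented; "The first site visit may be after 8 weeks before starting the 16-week schedule to align individual visit schedules with endpoints".

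**Check of the fix.** The rule and its replacement were run over every positive/negative pattern on the 4-week schedule. The switch between schedules was set every 8 weeks and no later than Week 140 (the maximum treatment duration to May 2021). EOT was set at even weeks from 18 to 268, at most about 158 weeks after the switch (May 2021 to May 2024 is 156.6 weeks, plus 2). In these 1,382 combinations, 1,646 patterns move from transient to indeterminate. Some move from transient to persistent, but only if the rule had been read as adjacent pairs. None leaves persistent or indeterminate. These counts describe the rule; they are not subject frequencies.

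**The case against.** The strongest reply is that little depends on this. The three labels are exhaustive and the same in both documents, and 'transient' is openly defined as a residual. SAP section 2 specifies no testing. The yes/no ADA endpoint, the main ADA categories and the primary endpoint do not change. The ADA-by-adverse-event summaries are optional in protocol 14.3.8.4 and not repeated in SAP 5.8.6. Subjects with a positive ADA sample are also plotted and listed individually. All of this stands, and it is why the point is minor.

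A second reply is comparability. SAP 5.9 reports several earlier analyses, including a comprehensive safety report to EMA. The documents do not say whether these used the subcategories. If they did, a late change of definition needs a note.

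Two stronger readings are tempting and not supported:

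- A reader might infer that many subjects are mislabelled, since EOT plus SFU positive is transient for every EOT week. That is a single comparison, 2 weeks against 10, repeated for each week. The documents give no ADA incidence or onset times from which to derive a number.
- A reader might infer that the 16-week group is free of the problem. That holds only for subjects with an EOT visit who attend SFU; late early termination or a missed SFU can still give 'transient'.

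**Conclusion.** The point holds as a minor flaw in the definitions. A treatment-emergent subject whose only positives form a final unbroken run of two or more samples spanning less than 10 weeks is labelled transient without any later negative sample. With visits in window on the 4-week follow-up this is certain for EOT plus SFU and for early termination plus SFU, under either reading of the 10 weeks. It also occurs when the preceding ADA visit is positive and EOT follows 2 to 6 weeks later.

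The result rests on visits being held in window and on earlier samples being negative. It would fail for the two-sample cases only if SFU were held 10 weeks or more after EOT or early termination, a gross departure from that schedule. The number of subjects is unknown. The consequence is confined to the treatment-emergent subcategory table and any ADA-by-adverse-event summary built on it.

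**What to change.** Reword two definitions in SAP 5.8.6 and keep the third:

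- **Persistent:** an unbroken run of positive samples whose first and last samples are at least 10 weeks apart.
- **Indeterminate:** all positives confined to one final unbroken run that includes the last ADA sample and spans less than 10 weeks. A single positive at the last sample is the special case.
- **Transient:** the residual, as now.

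This also settles whether the 10 weeks refer to adjacent samples or to the whole run. No new data or table is needed. Some subjects move from transient to indeterminate, or to persistent if the rule had been read as adjacent pairs. Subjects with intermittent positives stay transient.

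Two costs remain. Labels will still differ between the 4-week and 16-week groups, because the observed follow-up differs. If earlier interim reports used the present subcategories, a footnote to the table should state the change, and SAP section 6 should list it as a departure from protocol 14.3.8.4.

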5.9 Interim analysis

At the time of writing this SAP several analyses have been conducted. Mainly, an interim report was prepared for EMA which delivered a comprehensive analysis focused solely on safety analyses. Japanese subjects in ECZTEND have been analysed for submission to PMDA. Several abstracts, posters, oral presentations, and articles have been presented and/or published featuring analyses from ECZTEND both in terms of safety and efficacy analyses on differing data-cuts.

6 Changes to analyses described in the protocol

Panel 5 summarises the changes to the analyses planned in the protocol.

Panel 5: Changes to the analyses described in the CTP

Section in the CTP	Description of change	Brief rational3
14.3.5	The specified strict NRI sensitivity analysis has been replaced by 2 sensitivity analyses.	The specified sensitivity analysis was not reasonable as it was not possible to distinguish causes based on the original intent, and due to the amendment extending the trial causing some subjects to not consent to continuing in the trial. A modified NRI method has been introduced as a replacement together with appropriate MI method.
14.3.5	No split on response vs non-response based on the last assessment in parent trials.	The last assessment is not necessarily representable of a fluctuating disease like AD and is conditioned by a lot of other factors, e.g. differing parent trial treatment periods and procedures.

Abbreviations: AD = atopic dermatitis; CTP = clinical trial protocol; MI = multiple imputation; NRI = non-responder imputation.

7 Supporting documentation

7.1 Tralokinumab naïve, re-treated, continuously treated, and washed-out subjects

For summary tables grouped by tralokinumab naïve, re-treated, continuously treated subjects the grouping is based on the following principle:

- *Tralokinumab naïve* subjects have not received any planned tralokinumab treatment in parent trial.
- *Continuously treated* subjects have had a period shorter than 16 weeks (5 half-lives of tralokinumab) between last tralokinumab administration in parent trial and first tralokinumab administration in ECZTEND.
- R*e-treated* subjects have had a period of 16 weeks or longer between last tralokinumab administration in parent trial and first tralokinumab administration in ECZTEND. Thus, full washout between treatment in ECZTEND and parent trial.

The combined group of tralokinumab naïve and re-treated subjects, which consists of those new to tralokinumab or washed out from tralokinumab will be called 'washed-out subjects'.

As data from the TRA-WEI-0015-I study have not been transferred to this study, subjects from the study will not be classified in these groupings.

7.2 Safety areas of interest

Two types of AESIs are defined:

- AESI: ECZTEND defined AESI (defined in the CTP Panel 15). These AEs are marked by the investigator in the eCRF, and these AEs require additional details to be recorded in the eCRF. See Panel 6.
- Tralokinumab ADRs: Defined using Adtralza[®] Company Core Data Sheet version 5.0, dated 14-Nov-2022. See Panel 7.

The searches described in this document are based on MedDRA version 27.0.

AESI*	Description
Eczema herpeticum	No additional description
Malignancy	Diagnosed after treatment assignment, excluding basal cell carcinoma, localised squamous cell carcinoma of the skin, and carcinoma in situ of the cervix.
Skin infections	Requiring systemic treatment.
Conjunctivitis**	No additional description
Keratoconjunctivitis**	No additional description
Keratitis**	No additional description

Panel 6: AESI: ECZTEND defined AESI

*: as defined in the CTP Panel 15; **: grouped in AESI 'Eye disorders'

Panel 7: Tralokinumab's ADRs

ADRs	Description
Upper respiratory tract infection	Preferred terms: Viral upper respiratory tract
	infection, Upper respiratory tract infection,
	Pharyngitis, Nasopharyngitis
Injection site reactions	All preferred terms under the high level term (HLT):
	Injection site reactions
Eosinophilia	Preferred terms: Eosinophilia, Eosinophil count
	increased
Conjunctivitis/Conjunctivitis allergic	Preferred terms: Conjunctivitis, Conjunctivitis allergic
Keratitis	Preferred terms: Keratitis

8 References

- 3. Lachin JM. Fallacies of last observation carried forward analyses. Clin Trials. 2016;13(2):161-168.
